- Have no prevalent diagnosis of Alzheimer's disease or related dementia and not previously screened for AD as part of a research study.
- Family members will be 21 years or older and identified by the patient as the person who would most likely assist with activities of daily living and/or medical decision making if the patient needed assistance.
- See Table 1 for patient and caregiver inclusion and exclusion criteria

Table 1. Inclusion and exclusion criteria for the proposed trial

Inclusion Criteria	
Patients	Family Members
65 years or older	21 years of older
At least one visit to primary care practice within past 24 months	Lives with the patient or lives within a 50 mile radius
Ability to provide informed consent	Ability to provide informed consent
Ability to communicate in English	Ability to communicate in English
	Identified by patient as the person most likely to provide them care if needed
Exclusion Criteria	
Patients	Family Members
Has a diagnosis of AD as determined by ICD-10 code	Is a non-family member who is not a legal Healthcare Power of Attorney
Evidence of a prescription for a cholinesterase inhibitors or memantine	
Has a serious mental illness such as bipolar or schizophrenia as determined by ICD-10 code	Has a serious mental illness such as bipolar or schizophrenia as determined by ICD-10 code
Permanent resident of a nursing facility	Has a diagnosis of AD as determined by ICD-10 code
Is already enrolled in HABC programs	

Recruitment Sites (as of 9/17/18):

- Indiana University Health Primary Care Practices
- Eskenazi Health Primary Care Practices

Primary outcome: Family member quality of life at 24 months.

Co-Primary outcomes: Family member depressive symptoms and family member anxiety at 24 months.

Co-Secondary outcomes: Family member caregiving preparedness and caregiving self-efficacy at 24 months.

Exploratory outcome: Comparison of all outcomes (noted above) between the family members in Screen Only vs. Screen Plus groups.

Table 2. Measures

Outcomes	Construct/Core Attributes	Outcome measure(s)	Name of Measure	Description	Scoring	When	Source
Primary outcome	Family member Quality of Life	Quality of Life	Medical Outcomes Study Short Form Health Survey 36 (SF-36)	36-items that measure health-related quality of life, mental, physical, and social functioning	Scores range 0-100; Higher scores more QOL	Baseline 6 mos. 12 mos. 18 mos. 24 mos.	Family reported Patient reported

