Participants will be recruited from primary care offices affiliated with Eskenazi Health and IU Health.

Step 1: Identification of Potential Participants

- Participants will be identified in a variety of ways and will be tailored based on the recruitment site. Patients will be identified via the Indiana Network for Patient Care, (INPC) which can access patient lists by doctor, clinic, and PC clinic schedules. Physicians will be notified first of their patients' potential eligibility and be asked if the COADS study personnel may approach the patient and their family member for participation. Physicians are routinely given 2 weeks to review the list of their potentially eligible patients (per IU PBRN). Physicians will be given the opportunity to opt-out of study participation at this time. Following either approval from the PCPs, or at the end of the two-week review period study personnel will mail out an introductory letter, email or post card to patients. Study personnel will then approach patients via telephone, email or in person in the-clinic to confirm eligibility and obtain informed consent.
- We will consider any man or woman 65 years or older who has not been diagnosed with AD or related dementia, and is considered an active patient (PCP visit in- person or virtual within 24 months including requests for prescription refills, or questions and is able to provide consent, and speaks English.

- We will approach the primary family member/caregiver/informant for each eligible participant. Family members will be eligible if they are patient-identified or self-identified as a person who is likely to provide care for the patient, is 21 years or older, lives within a 50-mile radius of the participant, is able to consent, and speaks English
- Rolling enrollment will take place over 36 months with an average monthly recruitment of 50 dyads

Step 2: Enrollment

- Following eligibility determination and the informed consent process (including HIPAA release), dyads will be randomly assigned to one of three groups, stratified by site (e.g. Eskenazi or IUH). Dyads are officially enrolled at this point.

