- **Multi-level mixed effects models** will be used to examine differences in SF-36 scores for both patients and family members using dyadic analytic approaches. For this aim, we will compare family members in the two screening groups (Screen Only and Screen Plus) to those in the no screening (Control) group. Repeated SF-36 scores from both patients and family members will be included as the outcome variables with participant type (patient or family member), group (Screening Only and Screening Plus versus Control), time, and interaction between groups and time as independent variables. We will use a multi-level variance-covariance matrix in the mixed effects models to account for two sources of potential correlations. Correlations from measures obtained from the same individual over time, an autoregressive correlation will be used. Correlations within a dyad between a patient and his/her family member. A compound symmetry structure will be used for the within-dyad correlation. Parameter estimation and hypothesis tests for the mixed-effects models will be conducted using the maximum likelihood approach that provides robust estimation under the missing at random mechanisms.
- A significant interaction between group and time would indicate differences in changes of SF-36 over time between the two screening groups compared to the no screening group. Absence of significant interactions, significant main group effects will suggest differences in SF-36 between groups' at all follow-up times. For Hypothesis 1 we will use a linear contrast for SF-36 from family members in the combined screening groups (Screen Only and Screen Plus) versus the no screening (Control) group at 24 months. We will also include additional covariates in the mixed effects models to determine whether family member characteristics (relationship to patient, frequency or types of contact, etc.) and knowledge of screening are associated with the outcome measures.

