- The multi-level mixed effects models provide a powerful modeling framework for analyzing dyadic outcomes. An alternative model using family member outcomes as the dependent variable and patient outcomes as an independent variable would underestimate variances in outcome measures by ignoring the randomness in the patients' outcomes by treating patient outcomes as fixed covariates. In our proposed models, correlations between patients and their family members on outcome measures (congruence) are explicitly included in the mixed effects models and estimated using maximum likelihood approach. The inclusion of the additional covariance structure due to repeated measures and within dyad correlation also makes it possible to estimate potential differences in patient-family member congruence over time. Comparisons on patient-family member congruence among the groups will be conducted using the likelihood ratio test (LRT) derived from a mixed effects model using group specific correlation structure versus a model using the same correlation in all groups. Changes in congruence can also be conducted using LRT comparing a mixed effects model with time specific correlation structure versus a model using equal correlations across time. By re-aligning data from the family member at specific lag time behind measures from patients, we will also be able to detect a lag effect in family member outcomes using this modeling framework.

Secondary Aim

- **Separate mixed effects models** with PHQ-9 or GAD-7 scores collected at baseline, 6, 12, 18 and 24 months from both patients and family members will be used as the outcome variables for Specific Aim 2. Participant type, randomized group (Screen Only and Screen Plus versus no screening), time and interaction between group and time will be used as independent variables, similarly to the modeling procedures described in details for Aim 1 above. Linear contrasts will be used to compare PHQ-9 and GAD-7 scores from family members in the combined screening groups versus the no screening group at 24 months. Dyad congruence in PHQ-9 and GAD-9 will be examined using LRT from the mixed effects models following the procedure described for Aim 1.

Secondary Aim

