- **Mixed effects models with Caregiver Preparedness Scale or the Revised Scale for Caregiver Self-Efficacy scores** collected at baseline, 6, 12, 18 and 24 months will be used as the outcome variables, group (Screen Only and Screen Plus versus Control), time and interaction between group and time as independent variables. Linear contrasts will be used to compare preparedness and caregiver self-efficacy scores in the combined screening groups versus the no screening group at 24 months. We will also evaluate potential interactions between patient's/family member characteristics and variables associated with increased level of caregiver preparedness and self-efficacy over time.

Secondary Aim

- **To measure the impact and compare strategies for evaluation and treatment post screening, we will compare quality of life measures, caregiver preparedness, caregiving self-efficacy, depression and anxiety symptoms from family members** in the Screen Only (notify dyad and PCP of results only) group to the Screen Plus (notify dyad and PCP and a referral to ABC Program if screen positive) group using multi-level mixed effects models, similarly to the approach described in details for Aim 1. Separate mixed effects models with SF-36, Caregiver Preparedness Scale, Revised Scale for Caregiver Self-Efficacy, PHQ-9 or GAD-7 scores collected at baseline, 6, 12, 18, and 24 months from family members will be used as the outcome variables. Screening group (Screening Only versus Screening Plus), time and interaction between group and time will be used as independent variables. Linear contrasts will be used to compare all scale scores between the two screening groups at 24 months.

Sensitivity analyses for the impact of refusals and other sources of missing data

- We will compare patient and family member characteristics between those who complete at least one or more follow-up assessment(s) after baseline and those who did not complete any assessment beyond baseline due to refusal or other reasons. Significant variables detected from these comparisons will be included in the mixed effects models for the primary and secondary outcomes as covariates to control for potential bias from those missing follow-up outcomes. Under the missing at random

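### Site stratifies the randomisation but is in no outcome model, and the 24-month contrasts leave group baselines free: a minor, nearly free improvement

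*Combined protocol and SAP*

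**What the plan says.** - **Randomisation.** Under Step 2: Enrollment, dyads are "randomly assigned to one of three groups, stratified by site", with the two health systems as the example. The list headed "Recruitment Sites (as of 9/17/18" names the same two systems.
- **Aim 1 model** (Statistical Plan, Primary Aim). Repeated SF-36 scores of patients and family members are the outcome. The terms are participant type and "group (Screening Only and Screening Plus versus Control), time, and interaction between groups and time as independent variables". Further covariates are mentioned for an association question; site is not among those named.
- **Aim 2 model** (first Secondary Aim). Participant type and "randomized group (Screen Only and Screen Plus versus no screening), time and interaction between group and time will be used as independent variables".
- **Aims 3 and 4 models.** Group, time and their interaction. Site is not named here either.
- **Hypothesis tests.** "For Hypothesis 1 we will use a linear contrast for SF-36 from family members in the combined screening groups" against control at 24 months. Likewise "Linear contrasts will be used to compare PHQ-9 and GAD-7 scores from family members in the combined screening groups" for Aim 2 and "Linear contrasts will be used to compare preparedness and caregiver self-efficacy scores in the combined screening groups" for Aim 3. Aim 4 compares the two screening arms in the same way.
- **Interaction test.** "A significant interaction between group and time would indicate differences in changes of SF-36 over time". The Statistical Power section is written for this test.
- **Missing data.** The sensitivity section adds covariates that differ significantly between those with and without follow-up. Site could enter by that route, but only if the data happened to select it.

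**The concern.** When randomisation is stratified, the arms are balanced on the stratum by design. A model without the stratum still counts the between-site variation as noise, so its standard errors are larger than the true sampling variation of the group difference. The test is then conservative and some precision is lost.

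In a model with group, time and group-by-time, each group has its own baseline mean. The 24-month contrast is therefore a difference in levels, and a share of any chance baseline difference, in proportion to the baseline-to-24-month correlation, remains in it. Since randomisation makes the true baseline means equal, a model can use that fact to remove the share.

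What is at stake is precision. A stable site effect cancels in changes over time, and the interaction test already compares changes. So both points concern the 24-month contrasts, and the site point also concerns the main group effect.

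**Working it through.** **Inputs from the plan.** 540 dyads per arm with complete data, so 1,080 screened against 540 controls; effect sizes 0.24 SD (Aims 1-3) and 0.28 SD (Aim 4); five visits; linear exponent autoregressive correlation with base 0.2 and decay 0.8. **Assumed:** two-sided alpha 0.05 (not stated in the plan), SD 1, complete data, and the site shares and higher correlations given below.

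**1. The plan's own power figures.** The correlation at a lag of j visits is 0.2^(1 + 0.8(j-1)/3), which gives 0.200, 0.130, 0.085 and 0.055 for lags 1 to 4. Let the group difference grow linearly from 0 at baseline to its 24-month value, and test group-by-time with a 4-df multivariate F test. Power is 82.61% for 0.24 SD (stated 82.6%) and 83.42% for 0.28 SD (stated 83.4%). The structure is read correctly, and the stated power belongs to a 4-df interaction test. The plan's baseline-to-24-month correlation is thus 0.055.

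**2. Reference precision.** Raw 24-month difference: SE = sqrt(1/540 + 1/1080) = 0.0527 SD.

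**3. Site omitted, family-only models (Aims 3-4).** If site explains a share R2 of variance, the reported SE is too large by the factor 1/sqrt(1-R2), and type I error is 2(1 - Phi(1.96/sqrt(1-R2))).
- R2 = 1%: 1/sqrt(0.99) = 1.005, so +0.5%; type I error 4.9%.
- R2 = 5.5%: 1/sqrt(0.945) = 1.029, so +2.9%; type I error 4.4%.

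The documents give no site variance. The upper value is chosen because a stable site effect alone produces a baseline-to-24-month correlation of at least R2, so a larger share would conflict with 0.055.

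**4. Site omitted, pooled models (Aims 1-2 as listed).** These models have one group effect for both members, so the relevant variance is that of the dyad mean, (1+r)/2, with r the within-dyad correlation. With the same site effect in both members, the site share becomes s = R2/((1+r)/2), and s replaces R2 in the formulas of step 3. The values of r are assumed.

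| R2 | r | s | SE too large by | Type I error |
|---|---|---|---|---|
| 1% | 0.5 | 0.0133 | 0.7% | 4.8% |
| 1% | 0.055 | 0.0190 | 1.0% | 4.8% |
| 5.5% | 0.5 | 0.0733 | 3.9% | 4.2% |
| 5.5% | 0.055 | 0.1043 | 5.7% | 3.8% |

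**5. Equal-baseline constraint.** Variance of the 24-month contrast relative to the raw difference:
- Time as categories, plan's correlations: free 1.000; constrained 1 - 0.055^2 = 0.997. Cut: 0.3%.
- Linear time, plan's correlations (generalised least squares): free 0.720; constrained 0.707. Since 0.707/0.720 = 0.982, the cut is 1.8%.
- Categories, assumed correlation 0.5: 1 - 0.25 = 0.750, a cut of 25%. Assumed 0.7: 1 - 0.49 = 0.510, a cut of 49%.

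In the pooled model the ratios 0.997 and 0.982 are unchanged for within-dyad correlations from 0 to 0.5.

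**6. Chance imbalance.** A baseline difference of two standard errors is 2 x 0.0527 = 0.105 SD. The part carried on average into the free 24-month contrast is correlation x 0.105: 0.006 SD at 0.055, and 0.053 to 0.074 SD at 0.5 to 0.7.

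**7. Effect on power.** At 0.24 SD the categorical 24-month contrast already has 99.52% power. With baseline used at correlation 0.055, it has 99.53%.

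**The case against.** **The gains are immaterial on the plan's own figures.** This largely stands. Power of the 24-month contrast barely moves, the site error is on the conservative side, and the larger baseline gains rest on correlations that the documents do not give. The site range is also assumed. Its 5.5% ceiling depends on the 0.055 correlation, so it would not apply in the 0.5-0.7 scenario. At an assumed 10% share the family-only type I error would be 3.9%. This limits the benefit but does not remove it, since the cost is wording.

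**Free baseline means are a standard longitudinal model, and the interaction test already compares changes.** True, and this is why the baseline point is confined to the 24-month contrasts.

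**Forcing equal baselines is safe only if allocation cannot affect baseline scores.** This stands, and it conditions the fix. Step 2 randomises after consent and then has the patient screened at baseline. Table 2 lists the outcome scales at baseline without saying whether they come before allocation or before the screen. If they come after, the constraint could remove part of a real effect, most of all at the high correlations where it would gain most.

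**Baseline as a covariate would disturb the congruence analyses.** Also fair: those analyses use the repeated outcomes of both members over time. Keeping baseline in the outcome vector and constraining its group means avoids the problem.

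**A reader might infer that the constraint makes the interaction test and the 24-month contrast one test.** That would hold only for a one-degree-of-freedom change test. The plan's power figures belong to a 4-df test, which under the constraint would become a 4-df joint test of the follow-up visits. In 400,000 simulated trials on the plan's correlations, that joint test and the constrained contrast disagreed in 6.9% under the null and in 23% at a 24-month difference of 0.12 SD.

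**Conclusion.** The point holds as a minor, nearly free improvement. The analysis does not follow the stratified design, and the 24-month contrasts do not use the fact that randomised groups start equal. The site error is certain in direction (standard errors too large, test conservative) if site is related to outcome. Its size, 0.5-5.7% across the two kinds of model, rests on an assumed site share of 1-5.5%, a stable additive site effect and, in the pooled models, assumed within-dyad correlations. The baseline gain is negligible at the plan's correlation of 0.055 and worthwhile only if the true correlation is much higher.

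Two stronger readings are not supported. A reader might infer that the omissions bias the results or inflate false positives. They do neither: randomisation protects the comparison, and type I error falls below 5%. A reader might also infer that the trial ignores baseline altogether. It does not: baseline is in the outcome vector, and the group-by-time test removes baseline differences by differencing.

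**What to change.** 1. Add site, as used in the randomisation, as a fixed effect in every outcome model for Aims 1 to 4. This costs one degree of freedom if the strata are the two named health systems.
2. State when baseline outcome scores are collected relative to allocation and to the patient's cognitive screen.
3. If they are collected before allocation is known and before the patient is screened, take each 24-month contrast from a model that constrains group means to be equal at baseline and keeps baseline among the repeated outcomes. The congruence analyses are then unaffected. If they are not, leave the baseline means free and make only the site change.
4. Keep the 4-df group-by-time test as a separate analysis, with its power statement unchanged.

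The cost is wording in the statistical plan, plus the check in item 2. Site and baseline scores are already collected.

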assumption, results from the mixed effects models will remain unbiased if the variables contributing to the missing data are included as covariates in the models. We will also perform additional sensitivity analyses to examine whether the missing at random assumption using the selection model approach under an informative missing mechanism impacts our analyses.

Statistical Power

Sample Size and Power Considerations for COADS

For the models in Aims 1, 2 and 3, we assume a base correlation of 0.2 and a decay rate of 0.8 in a linear exponent autoregressive correlation structure for repeated measures and a continuous time response, we will need to have 540 dyads per group to have complete data at 24 month in order to achieve 82.6% power to detect a group by time interaction with an effect size of 0.24 SD with higher SF-36, lower PHQ-9, GAD-7, higher caregiver preparedness and self-efficacy scores at 24 months in the combined screening groups (Screen Only and Screen Plus) compared to family members in the no screening (Control) group. Our previous screening studies and studies in primary care had a 5% loss to follow-up (death or withdraw) within a 12-month period. Therefore, allowing a loss to follow-up rate of 10% over the 24 months, we plan to enroll 600 dyads per group into this study. For Aim 4, using similar assumptions on the correlation structure for repeated measures and also 10% attrition rate, we will have 83.4% power to detect a significant group and time interaction with an effect size of 0.28 SD comparing family members randomized to the screening plus group to those in the screening only group at 24 months. Power estimation was conducted using the GLM Power procedure in SAS.

Timeline

Table 3. Study Timeline	Year 1	Year 2	Year 3	Year 4	Year 5
Hire/ train staff					
Revise protocol manual and database					
IRB modification and approval					
Subject recruitment and consent					
Data collection					
Data analysis					
Prepare abstracts and manuscripts					
Disseminate results

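### Once the 24-month contrast is made specific to family members, a single-variance compound symmetry structure gives it a wrong standard error if patients and family members differ in variance; the fixed effects and the covariance need changing together.

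*Combined protocol and SAP*

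**What the plan says.** Under Primary Aim, SF-36 scores from both dyad members are the outcome of one model. The fixed effects are participant type, plus "group (Screening Only and Screening Plus versus Control), time, and interaction between groups and time as independent variables". Participant type enters as a main effect only.

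On the covariance, the plan says: "We will use a multi-level variance-covariance matrix in the mixed effects models to account for two sources of potential correlations". Within a person: "Correlations from measures obtained from the same individual over time, an autoregressive correlation will be used". Within a dyad: "A compound symmetry structure will be used for the within-dyad correlation". Estimation and tests are "conducted using the maximum likelihood approach that provides robust estimation under the missing at random mechanisms"; that robustness refers to missing data, and no empirical (sandwich) SE is named.

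The test of the first hypothesis is set out as follows: "we will use a linear contrast for SF-36 from family members in the combined screening groups (Screen Only and Screen Plus) versus the no screening". The time point is month 24. The Aim 2 section applies the same model to PHQ-9 and GAD-7, "similarly to the modeling procedures described in details for Aim 1 above", again with a contrast among family members. The congruence paragraph lets correlations differ by group and by time but does not mention variances by participant type.

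The Aim 3 outcomes are reported by family members only, and the Aim 4 models use family-member scores only, so neither is affected.

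**The concern.** Patients are 65 or older and family members 21 or older, so there is no reason to take equal spread on SF-36, PHQ-9 or GAD-7 for granted. In its usual form, compound symmetry has one variance and one covariance. A contrast that uses only family-member data would then take its SE from a variance averaged over both members.

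If patients vary less than family members, the confidence interval is too narrow and the test too liberal. If they vary more, the interval is too wide and power is lost. Sample size does not help, because the averaged variance is estimated precisely but is the wrong quantity. The outcomes at stake are quality of life and the two listed with it as co-primary, depressive symptoms and anxiety.

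**Working it through.** **Inputs.** From the documents: 540 completing dyads per group ("we will need to have 540 dyads per group to have complete data at 24 month"), so 1,080 screened against 540 controls; five visits; autoregressive by compound symmetry covariance; the fixed effects above. Assumed, because not given: two-sided alpha 0.05; k = patient SD / family-member SD from 0.7 to 1.5; within-dyad correlation ρ of 0, 0.3 or 0.5. The family-member SD is set to 1.

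**The plan's own figure.** A multivariate F test of group by time (4 numerator df) was run with the plan's linear exponent autoregressive correlation (base 0.2, decay 0.8) and a difference growing linearly from 0 to 0.24 SD. With 1,080 vs 540 it gives 82.6%. With 0.28 SD and 540 vs 540 it gives 83.4% for Aim 4. Both match the plan. Neither uses a patient variance, so this point does not change them.

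**What the single-variance model estimates.** Its maximum likelihood limit has variance s² = (1 + k²)/2, the mean of the two variances, and the true covariance ρk. Let B² = 1/1080 + 1/540 = 0.002778, so B = 0.0527. The formulas below take time as categorical and data as complete.

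**(a) Fixed effects as listed.** With no participant type by group by time term, the 24-month contrast is the equal-weight average of the patient and family-member differences.
- True variance: B²(1 + k² + 2ρk)/4.
- Model variance: B²(2s² + 2ρk)/4 = B²(1 + k² + 2ρk)/4.

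These are identical. The SE ratio is 1.0000 for every k from 0.7 to 1.5 and each ρ, with time categorical or linear, and type I error stays at 5%.

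**(b) Participant type by group by time added.** The contrast now uses the family-member difference alone.
- True variance: B².
- Model variance: B²s².
- SE ratio: sqrt((1 + k²)/2), whatever ρ is. Type I error: 2(1 − Φ(1.96 × ratio)).

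| k | s² | Model SE | True SE | Ratio | Type I error |
|---|---|---|---|---|---|
| 0.7 | 0.745 | 0.0455 | 0.0527 | 0.863 | 9.1% |
| 0.8 | 0.820 | 0.0477 | 0.0527 | 0.906 | 7.6% |
| 0.9 | 0.905 | 0.0501 | 0.0527 | 0.951 | 6.2% |
| 1.0 | 1.000 | 0.0527 | 0.0527 | 1.000 | 5.0% |
| 1.1 | 1.105 | 0.0554 | 0.0527 | 1.051 | 3.9% |
| 1.25 | 1.281 | 0.0597 | 0.0527 | 1.132 | 2.7% |
| 1.5 | 1.625 | 0.0672 | 0.0527 | 1.275 | 1.2% |

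With linear time the SEs are slightly smaller, but the ratios are the same.

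**Dropout check.** Simulation at ρ = 0.3, with about 10% family-member and 15% patient dropout:
- Model (a): ratio 0.997 at k = 0.7 (600 runs) and 1.05 at k = 1.5 (150 runs, Monte Carlo error about 6%).
- Model (b): 0.85 and 1.29 (150 runs each).

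**(c) Covariance changed alone.** Keep the listed fixed effects but allow two variances. The family-member weight in the contrast becomes (k² − ρk)/(1 + k² − 2ρk). At ρ = 0.3:
- k = 0.7: 0.28/1.07 = 26%.
- k = 1.5: 1.80/2.35 = 77%.

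Neither is 100%, and the first is further from family members than the 50% under (a).

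**The case against.** A reader might infer that the SE of the primary contrast is wrong whenever the two variances differ. The documents do not support that. For the fixed effects they list, case (a) shows the SE to be right with complete data, and the simulation shows no clear departure with dropout. This part of the objection stands. It does not rescue the plan, because that SE belongs to a patient-and-family average, whereas the text promises a contrast among family members. Adding the missing terms and leaving the covariance alone leads straight to case (b).

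Second, equal variances are inferred, not stated. The sentence sets a structure for the correlation, and for two people a compound-symmetric correlation is a single number that can sit beside two variances. This also stands: the plan is under-specified rather than explicit. But single variance is the usual meaning of the term, nothing in the plan points elsewhere, and the choice decides the SE of a family-specific contrast.

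Third, the practical loss may be small. For a simple family-member comparison at 24 months with 0.24 SD, nominal power is 99.5% at k = 1 and still 98.0% at k = 1.5. That answers the conservative direction only. It does not answer a type I error of 9.1% at k = 0.7.

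**Conclusion.** The point holds conditionally. As listed, the joint model has a valid SE for an average over both dyad members, which is not the stated contrast. Made family-specific under single-variance compound symmetry, the contrast has an SE off by the factor sqrt((1+k²)/2): 0.86 to 1.27 over the assumed range of k, with type I error about 9% to 1%, and no error at k = 1.

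This rests on reading compound symmetry in its usual sense, on model-based SEs, on two-sided alpha 0.05 and on an assumed range for k. Because no SD is given for either member, the documents cannot show whether the error would be liberal, conservative or nil. They do not support saying that the planned primary test has an inflated type I error, or that the sample size is wrong.

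**What to change.** In the joint models for SF-36, PHQ-9 and GAD-7, make two changes together:

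1. Add participant type by group by time, with its lower-order terms (participant type by group, participant type by time).
2. Replace the within-dyad block by an unstructured or heterogeneous 2×2 block, with separate patient and family-member variances and their covariance; for example UN@AR(1) in SAS PROC MIXED.

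Take the 24-month family-member contrast and its SE from that model. As case (c) shows, the second change alone only re-weights the patient-family blend; the first alone exposes the SE error.

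The cost is one extra variance parameter and some fixed effects: 3 with a two-level group and linear time (1 + 1 + 1), up to 14 with three arms and five categorical visits (2 + 4 + 8). These would be estimated from about 1,800 dyads, with no new data. The family-specific SE is larger than that of the pooled average in most scenarios: at ρ = 0.3, 0.0527 against 0.0364 (k = 0.7) or 0.0425 (k = 1), though slightly smaller than 0.0537 at k = 1.5. That is the price of estimating the stated quantity.
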